10.1.2.4. Unsolicited adverse events

Unsolicited adverse event summaries are including serious adverse events unless specified otherwise.

Missing relationship with study vaccine, and outcome of unsolicited adverse events will not be replaced and will appear as 'UNKNOWN' when displayed in a statistical output.

Missing severity will follow the next imputation rules:

- *If serious adverse event = 'Y' then severity = 'Severe'*
- *If serious adverse event = 'N' and action taken with study vaccine(s) as a result of the event = 'Dose not changed' and subject did not withdraw from the study due to this event, then severity = 'Mild'*
- *If previous two rules were not applicable, then severity = 'Moderate'*

10.1.3. Data derivation

10.1.3.1. Age at first dose in years

When age at first dose is to be displayed in years, it will be calculated as the number of complete calendar years between the date of birth and the date of first dose. For example:

DOB = 10SEP1983, Date of first dose = 09SEP2018 -> Age = 34 years

DOB = 10SEP1983, Date of first dose = 10SEP2018 -> Age = 35 years

10.1.3.2. Temperature

Temperatures will be presented in degrees Celsius (°C). Temperatures reported in degrees Fahrenheit (°F) will be converted as follows:

$$\text{Temperature (Celsius)} = ((\text{Temperature (Fahrenheit)} - 32) \times 5)/9$$

10.1.3.3. Onset day

The onset day for an event (e.g. AE, medication, vaccination) is the number of days between the last study dose and the start date of the event. This is 1 for an event occurring on the same day as a study dose (and reported as starting after first dose).

10.1.3.4. Duration of events

The duration of an event with a start and end date will be the difference between the start and end date plus one day, i.e. an event that starts on 03MAR2018 and ends on 12MAR2018 has a duration of 10 days.

The duration of solicited events will be calculated as the sum of the individual days with the adverse event reported at grade 1 or higher during the solicited event period.

If symptom is ongoing and the end date of event is partially or fully missing, end date will not be imputed for the calculation of duration.

10.1.3.5. Counting rules for combining solicited and unsolicited adverse events

For output combining solicited and unsolicited adverse events, all serious adverse events will be considered systemic events since the administration site flag is not included in the expedited adverse event CRF pages. Unsolicited adverse events with missing administration site flag will also be considered systemic.

Multiple events with the same preferred term which start on the same day are counted as only one occurrence.

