12.5.2. Definition of SAE

A SAE is any untoward medical occurrence that:

- Results in death,
- Is life-threatening,

Note: The term 'life-threatening' in the definition of 'serious' refers to an event in which the subject was at risk of death at the time of the event. It does not refer to an event, which hypothetically might have caused death, had it been more severe.

- Requires hospitalization or prolongation of existing hospitalization,

Note: In general, hospitalization signifies that the subject has been admitted at the hospital or emergency ward for observation and/or treatment that would not have been appropriate in the physician's office or in an out-patient setting. Complications that occur during hospitalization are also considered AEs. If a complication prolongs hospitalization or fulfils any other serious criteria, the event will also be considered

serious. When in doubt as to whether 'hospitalisation' occurred, or was necessary, the AE should be considered serious.

- Hospitalization for elective treatment of a pre-existing condition (known or diagnosed prior to informed consent signature) that did not worsen from baseline is NOT considered an AE.

- Results in disability/incapacity, OR

Note: The term disability means a substantial disruption of a person's ability to conduct normal life functions. This definition is not intended to include experiences of relatively minor medical significance such as uncomplicated headache, nausea, vomiting, diarrhoea, influenza like illness, and accidental trauma (e.g. sprained ankle) which may interfere or prevent everyday life functions but do not constitute a substantial disruption.

- Is a congenital anomaly/birth defect in the offspring of a study subject

Medical or scientific judgement should be exercised in deciding whether reporting is appropriate in other situations, such as important medical events that may not be immediately life-threatening or result in death or hospitalization but may jeopardize the subject or may require medical or surgical intervention to prevent one of the other outcomes listed in the above definition. These should also be considered serious.

Examples of such events are invasive or malignant cancers, intensive treatment in an emergency room or at home for allergic bronchospasm, blood dyscrasias or convulsions that do not result in hospitalization.

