5.7. Analysis of safety and reactogenicity

5.7.1. Analysis of safety and reactogenicity planned in the protocol

The primary analysis of safety will be performed on the ES. All analyses will also be performed by age strata (50-69 YOA and ≥ 70 YOA). Following analysis is planned to be performed:

The percentage of subjects with at least 1 local AE (solicited and unsolicited), with at least 1 general AE (solicited and unsolicited) and with any AE (solicited and unsolicited) during the solicited follow-up period will be tabulated with exact 95% CI after each vaccine dose and overall. The percentage of doses followed by at least 1 local AE (solicited and unsolicited), by at least 1 general AE (solicited and unsolicited) and by any AE will be tabulated, with exact 95% CI. The percentage of subjects with at least 1 local AE (solicited only), with at least one general AE (solicited only) and with any AE (solicited only) during the solicited 7-day follow-up period will be tabulated with exact 95% CI after each vaccine dose and overall.

The percentage of subjects reporting each solicited local and general AE during the solicited follow-up period will be tabulated with exact 95% CI. The percentage of doses followed by each individual solicited local and general AE will be tabulated, with exact 95% CI. Fever will be reported *with any ($>=38.0$), $>=38.0 - <=38.5$, $>38.5 - <=39.0$ and >39.0 in GSK scale. In Chinese scale, it will be reported with any ($>=37.3$), $37.3 - <38.0$, $38.0 - <38.5$, $38.5 - <39.5$ and $>=39.5$* . The same tabulation will be performed for fever with causal relationship to the study vaccine.

*In the table presented based on the GSK scale, for all other solicited AEs, the same table will have grade 1, grade 2 and *at least* grade 3 AEs and for any and *at least* grade 3 general AEs with relationship to the study vaccine. Related grade 1 and related grade 2 will also be displayed.*

In the table presented based on the Chinese scale, for all other solicited AEs, the same table will have grade 1, grade 2, grade 3 and grade 4 applicable for table with Chinese intensity scale) AEs and for any, grade 3 and grade 4 general AEs with relationship to the study vaccine. Related grade 1 and related grade 2 will also be displayed.

The proportion of solicited AEs resulting in a medically attended visit will be tabulated.

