9.2.3. Safety

- For the analysis of HZ related complications/unsolicited AEs/SAEs/pIMDs/concomitant medication, all vaccinated subjects will be considered and subjects who did not report an event will be considered as subjects without an event.
- AEs that need to be reported as pIMDs are listed in Table 23 of the protocol. *The table presenting pIMDs, will also include the AEs considered as pIMDs as per MedDRA dictionary.*
- Assessment of intensity for solicited local and general AEs will be done separately as per GSK scale and Chinese scale. From an analysis perspective, the intensity of nausea, vomiting and diarrhoea will be presented separately as per the guidelines of Chinese authorities. In addition, as per GSK standard grading, the solicited general AEs of nausea, vomiting, diarrhoea and/or abdominal pain will be presented collectively as “gastrointestinal symptoms”.

For analysis as per GSK standard grading, the maximum intensity of any one of these solicited general AEs (i.e. nausea, vomiting and diarrhoea **and abdominal pain**) reported by a subject will be attributed as maximum intensity of “gastrointestinal symptoms” for that subject. Maximum of grade 3 and 4 will be considered as grade 3 **for all applicable solicited symptoms (not only gastrointestinal symptoms) in GSK standard grading table.**

The intensity of the following solicited AEs will be assessed as described below:

Table 3 Intensity scales for solicited symptoms in adults

Adults		
Adverse Event	Intensity grade	Parameter
Pain at injection site	0	None
	1	Mild: Do not influence or do slightly influence limb activities.
	2	Moderate Influence limb activities.
	3	Severe: Influence daily life.
	4	Lose the basic selfcare ability, or hospitalization
Redness at injection site		Record greatest surface diameter in mm
Swelling at injection site		Record greatest surface diameter in mm
Temperature*		Record temperature in °C (with 1 decimal)
Headache	0	Normal
	1	Mild: Headache that is easily tolerated
	2	Moderate: Headache that interferes with normal activity
	3	Severe: Headache that prevents normal activity
	4	Refractory; require emergency presentation or hospitalization
Fatigue	0	Normal
	1	Mild: Fatigue that is easily tolerated
	2	Moderate: Fatigue that interferes with normal activity
	3	Severe: Fatigue that prevents normal activity
	4	Emergency presentation or hospitalization
Gastrointestinal symptom (Diarrhea)	0	Normal

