***The solicited symptom diary card doesn't allow to choose grade 4 swelling or redness. Per team agreement, the grade 4 of swelling and redness will be identified when the below Preferred Terms (from MedDRA version 25.0) are reported as unsolicited adverse events within or ongoing 7 days post each dose:**

- **Dermatitis exfoliative**
- **Necrosis**

- ***Skin necrosis***
- ***Soft tissue necrosis***
- ***Abscess***
- ***Abscess sterile***
- ***Abscess limb***
- ***Abscess soft tissue***

Fever will be graded as:

Grade	GSK standard grading scale	Grading scale defined by Chinese authorities (for axillary measurement)
0	<38.0°C	<37.3°C
1	≥38.0°C –≤38.5°C	37.3°C –<38°C
2	>38.5°C –≤39.0°C	38.0°C -<38.5°C
3	>39.0°C	38.5°C - <39.5°C
4	Not defined	≥ 39.5°C

The preferred location for measuring temperature in this study will be the axilla. If temperature is measured by other routes (such as oral or rectal), fever grading as per GSK scale will remain the same irrespective of route of measurement. For the grading scale as per Chinese authorities, the following conversion will be used:

- Axillary temperature = Oral temperature minus 0.2°C;
- Axillary temperature = Rectal temperature minus 0.5°C.
- ***Axillary temperature = Tympanic membrane temperature***
- ***For the duration of solicited adverse event within the solicited symptom follow-up or total duration, the unknown or missing end date will not be imputed.***
- The definition of HZ related complication is described in section 12.5.2 of the protocol and is presented below:-

Post-herpetic neuralgia	PHN is defined by the presence of HZ-associated severe pain persisting or appearing more than 90 days after onset of the HZ rash.
Disseminated disease	Defined as ≥ 6 HZ lesions clearly outside the primary dermatome as per the investigator's judgment.
Ophthalmic disease	Defined as HZ affecting any eye structure as per the investigator's judgment.

Neurologic disease	Defined as cranial or peripheral nerve palsies, myelitis, meningoencephalitis, stroke, etc. that is temporally associated with an episode of HZ and, in the opinion of the investigator, is caused directly by VZV infection arising from the HZ episode.
Visceral disease	Defined as an abnormality of one or more internal organs (e.g., hepatitis, pneumonitis, gastroenteritis, etc.) that is temporally associated with an episode of HZ and, in the opinion of the investigator, is caused directly by VZV infection arising from the HZ episode

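### In tables that combine solicited and unsolicited AEs, every serious AE is counted as systemic, so a serious injection-site event enters the general row and can drop out of the local row

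*SAP*

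**What the plan says.** SAP 5.7.1 tabulates, for the solicited follow-up period, the share of subjects "with at least 1 local AE (solicited and unsolicited), with at least 1 general AE (solicited and unsolicited"). A further row counts any AE. Matching percentages are given by dose, and all safety analyses are repeated by age stratum.

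SAP 10.1.3.5 decides which row an event enters. In outputs that mix the two kinds of AE, "all serious adverse events will be considered systemic events since the administration site flag is not included in the expedited adverse event CRF pages". The reason given is thus a data limitation. A second default follows: "Unsolicited adverse events with missing administration site flag will also be considered systemic".

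Other parts of the plan foresee local events that are serious:

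- SAP 9.2.3, Table 3, defines grade 4 injection-site pain as "Lose the basic selfcare ability", or hospitalization. Protocol 12.5.2 lists "Requires hospitalization or prolongation of existing hospitalization" among the seriousness criteria.
- SAP 9.2.3 notes that the diary card cannot record grade 4 redness or swelling. On the Chinese scale that grade is assigned "when the below Preferred Terms (from MedDRA version 25.0) are reported as unsolicited adverse events" within, or ongoing in, the 7 days after a dose. The terms include abscess, skin necrosis and soft tissue necrosis. Seriousness is not a bar.
- SAP 10.1.2.4 includes SAEs in unsolicited summaries unless stated otherwise.

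**The concern.** Whether an event is local depends on where it occurs. Under 10.1.3.5 it depends on which CRF page was used: a non-serious injection-site event with a completed flag is local, and the same event becomes systemic once it is serious enough for the expedited page. The misplacement runs one way only, from local to general, and it affects the most serious local events.

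What is at stake is the accuracy of the combined local and general percentages, and agreement between tables in one report. A reader who finds a grade 4 local reaction in the Chinese-scale solicited table could find the same abscess counted as systemic in the combined table. No rule in the SAP reconciles the two.

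**Working it through.** The plan states no figure on this point, so there is nothing to reproduce. The check is a reading of the rules, followed by a scale calculation on assumed counts.

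**Step 1: scope.** The opening words of 10.1.3.5 limit the rule to combined outputs. In SAP 5.7.1 these are the combined local, general and any-AE percentages, by subject and by dose. Solicited-only tables, unsolicited tables by system organ class (SOC) and Preferred Term (PT), and SAE tables do not use the rule. SAP section 8 drops the causally related and at-least-grade-3 versions of the local/general/any-AE tabulations.

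**Step 2: what happens to one subject.** Each row counts subjects with at least one event of that type. Take one serious unsolicited injection-site event in the window:

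| Other AEs of the subject in the window | Local row | General row | Any-AE row |
|---|---|---|---|
| none | subject lost | subject added | unchanged |
| local only | unchanged | subject added | unchanged |
| general only | subject lost | unchanged | unchanged |
| local and general | unchanged | unchanged | unchanged |

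The same table applies by dose, and to a non-serious injection-site AE whose flag is blank.

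**Step 3: the same event in two tables.** Take an abscess at the injection site on day 5 that leads to hospital admission. Under SAP 9.2.3 its Preferred Term makes it grade 4 local redness or swelling on the Chinese scale. Under SAP 10.1.3.5 it is systemic in the combined table. The SAP does not say whether the derived grade 4 record also feeds the combined table. If it does, the subject stays in the local row but is still added to the general row.

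**Step 4: scale.** Inputs: about 3069 planned subjects per group (Protocol 7.2.2.2.1); 1228 to 1534 subjects targeted in the ≥70 stratum (Protocol Table 12), randomized 1:1; percentages shown to one decimal (SAP 10.1.4.1). The number k of affected subjects is an assumption. The largest shift of a row is 100 × k / n percentage points.

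- k = 1: 100 × 1/3069 = 0.03
- k = 3: 100 × 3/3069 = 0.10
- k = 10: 100 × 10/3069 = 0.33
- ≥70 stratum, per group: 1228/2 = 614 and 1534/2 = 767. For k = 1 the shift is 100/767 = 0.13 to 100/614 = 0.16.

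These are ceilings. Each requires the event to fall in the solicited window and the subject to have no other AE of the type concerned.

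**The case against.** The strongest defence is that this is a disclosed, treatment-neutral default with a stated reason. The missing flag is a real limitation: terms such as abscess, skin necrosis or abscess of a limb do not name an injection site, so coding alone cannot settle every case. The events are not hidden, because they remain in the SAE tables and listings and in the SOC/PT tables. The combined split is a planned tabulation, not one of the listed endpoints, and secondary analyses are descriptive. Table layouts sit in a separate document, so a footnote may already exist.

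All of that stands, and it keeps the point small. It does not justify a rule that places a known injection-site event in the general row. For grade 4 redness and swelling the SAP already uses Preferred Terms where the diary cannot supply the information.

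A reader might also infer that the rule contradicts the SAP's grade 4 definitions. The documents do not support that. Those definitions set intensity in the solicited tables, while 10.1.3.5 assigns local or systemic status in another table whose graded version has been dropped. Nor does hospitalised injection-site pain simply become systemic: pain recorded on the diary card is a solicited local AE and keeps the subject in the local row. What remains is inconsistent classification between tables.

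**Conclusion.** The point holds for the combined solicited-and-unsolicited outputs of SAP 5.7.1 and only there. A serious injection-site event, or an injection-site AE with a blank flag, is put in the general row. It leaves the local row when no other local AE covers that subject or dose. The effect is at most about 0.03 percentage points per affected subject in a group of 3069, and about 0.13 to 0.16 points in the ≥70 stratum. These figures rest on planned enrolment and an assumed number of events, since the documents give no rate.

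Three stronger inferences should be resisted:

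- That serious AEs are treated as systemic throughout the safety analysis. The rule is limited to combined outputs.
- That a separate count of unsolicited local AEs is understated. The SAP describes no such output; unsolicited AEs are tabulated by SOC and PT.
- That the error falls mainly on the RZV group. This may seem plausible for an adjuvanted vaccine, but the documents contain no figure for it.

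The correction is worth making because it is cheap and the error is systematic in direction, not because it could change the trial's conclusions.

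**What to change.** Amend SAP 10.1.3.5 along these lines: in outputs combining solicited and unsolicited AEs, SAEs and unsolicited AEs with a missing flag count as administration-site events (a) when the MedDRA Preferred Term names an injection, vaccination or administration site reaction, or (b) when blinded review, completed before unblinding, places an event whose term names no site (cellulitis, abscess, necrosis) at the injection site. All others remain systemic.

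Apply the same determination to the grade 4 redness/swelling rule in SAP 9.2.3, whose listed terms currently carry no site condition, so that the two tables agree. Footnote any reclassified SAE in the combined tables.

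The cost is a short SAP change, a term list and a brief blinded review of a few terms. No new data are needed. This is a table-counting rule and touches no clinical management.

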10.1.3.6. Counting rules for occurrences of solicited events

When the occurrences of solicited events are summarized, each event recorded as having occurred during a specific period will be counted as only one occurrence regardless of the number of days on which it occurs.

10.1.4. Display of decimals**10.1.4.1. Percentages**

Percentages and their corresponding confidence limits will be displayed with one decimal except for 100% in which case no decimal will be displayed.

10.1.4.2. Demographic/baseline characteristics statistics

The mean, median, and standard deviation for continuous baseline characteristics will be presented with one decimal.

The maximum and minimum of transformed body temperatures will be displayed with one decimal.

10.1.5. Statistical methodology**10.1.5.1. Exact confidence intervals around proportions**

The exact confidence intervals around within-group proportions are derived using the method of Clopper and Pearson [[Clopper](#), 1934].

10.2. TFL TOC

The Table Figure Listing (TFL) Table Of Content (TOC) which itemizes the planned list of TFL for final analysis with their associated lay-out is developed as a separate document.

